There is substantial overlap in mechanisms implicated in bipolar disorder and AUDs. Anxiety- and stress-related mechanisms are implicated in both bipolar disorder and AUDs with bipolar disorder comorbidity with anxiety disorder itself suggested to elevate the risk for comorbid AUDs [18]. This suggests changes in mechanisms and neural regions underlying stress modulation may be one path mediating the development of comorbid AUDs in bipolar disorder. There is significant genetic overlap across these disorders. For example, the 5'promoter region of the serotonin transporter gene (SLC6A4) has been associated with both bipolar disorder and anxiety disorders [19] and is suggested to be related to individual differences in responses to alcohol—an endophenotype that identifies young adults with high risk for alcohol use disorders [20]—including differences in the subjective high one feels following alcohol consumption [21] and reported number of drinks needed to feel intoxicating effects of alcohol [22]. These multiple (and potentially shared) mechanisms of disease may contribute to differences in disease progression that potentially may be targeted for treatment.

With these considerations in mind, the proposed research will focus on one mechanism for altering disease progression in adolescents and young adults with bipolar disorder. We will investigate whether differences in neural and self-reported subjective responses to alcohol, including stimulation and sedation responses, exist within individuals with bipolar disorder, compared to age-and sex-matched healthy comparison participants. Cognitive and behavioral data will be collected to control for appropriate factors and explore how cognitive (or other behavioral constructs) may be associated with these processes. Participants will first complete baseline structural and resting state functional magnetic resonance imaging (rsfMRI) and return within days of their baseline scan to participate in an alcohol challenge study that will directly investigate differences in neural and subject responses to alcohol, compared to placebo, in young adults with bipolar disorder and healthy comparison young adults. Identifying differences in neural responses to alcohol may enhance our understanding of why AUDs are more prevalent in bipolar disorder than the general population and may reveal novel therapeutic targets that can be targeted in future studies.

Our goals are to:

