A total of 60 bipolar and healthy comparison subjects (n=30 per group, 21-26 years of age, 50% women, with no history of a severe AUD) will be recruited from the greater Austin area. We included individuals with a history of mild/moderate AUDs as doing so is more generalizable since it is common that individuals in this age group experiment with alcohol use. We will exclude individuals with a history of symptoms suggesting dependence (which is what you see in individuals with severe AUDs). Subjects will be recruited through multiple venues to optimize subject enrollment. Once recruited and enrolled, subjects will undergo detailed structured clinical evaluations to verify inclusion and exclusion criteria followed by structural MRI assessments. Following standard beverage administration procedures, they will then complete measures of subjective response to alcohol and fMRI scans while under the influence of alcohol or a placebo condition (counter-balanced). All subjects will be euthymic and alcohol/placebo sessions will occur within 3 days of each other. fMRI assessments will include a continuous performance task with emotional and neutral distractors (CPT-END) and resting state scans. Participants will first complete the CPT-END task at baseline (outside the scanner) before their alcohol or placebo session. Our recent data suggest differences in ventral brain networks when viewing emotional stimuli for the first time compared to the second time (associated with habituation of emotional networks), but that there are minimal differences between the second and third viewings. We will investigate (Aim 1) differences in subjective response to alcohol between bipolar and healthy participants and associations with recent drinking patterns and (Aim 2) differences between bipolar and healthy young adults in alcohol-induced changes, compared to placebo, in regional activation in vPFC emotional networks and connectivity among these regions.

4 Data Analysis

Describe the data analysis plan, including any statistical procedures or power analysis.

To input text, click in the light grey area below.

Aim 1: Between Group Differences in Subjective Response to Alcohol

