Group (bipolar, healthy)-by-condition (alcohol, placebo)-by-time of subjective response interactions on subjective response to alcohol will be modeled, covarying beverage condition order, biological sex, and age with SEAS and DEQ subscale scores as the dependent variables. Time of subjective response (pre- and post-scan) and beverage condition (alcohol, placebo) will be within-subject factors and group an independent between-subject factor. Following no group-by-condition-by-time of subjective response interaction, the three-way interaction term will be dropped and group-by-condition interactions investigated. Following no two-way interaction, the two-way interaction term will be dropped and main effects of group and condition assessed. Findings for these planned analyses will be considered significant at $p < 0.05$.

Between Group Differences in Functional Connectivity to Alcohol

Using the CONN Toolbox, we will perform region of interest (ROI)-to-ROI bivariate correlation first-level analysis to calculate fisher transformed correlation coefficients (measure of functional connectivity (FC)) between a priori ROI-to-ROI connections during placebo and alcohol condition CPT-END fMRI sessions. We will extract Fisher transformed correlation coefficients between ROI-to-ROI connections during emotional stimuli and during squares for analysis. We will calculate the contrast: FC during emotional stimuli minus FC during squares for alcohol and placebo conditions, in line with prior studies. A priori ROIs will be defined using the FSL Harvard Oxford Atlas in the CONN toolbox, and included bilateral insula, amygdala, nucleus accumbens (NAcc), ventromedial PFC (vmPFC), lateral orbitofrontal cortex (OFC), subcallosal cortex (SCC), and inferior frontal gyrus pars triangularis (IFG.tri). We will examine ROI-to-ROI connections between limbic/subcortical regions (insula, amygdala, or NAcc) with ventromedial PFC (vmPFC or SCC) and ventrolateral PFC (OFC or IFG.tri) regions.

We will use a mixed model to examine group by condition by hemisphere (left, right) interactions on ROI-to-ROI FC response to emotional stimuli (contrast: emotional stimuli - squares). Group will be an independent between-subject factor, condition and hemisphere within-subject factors, and ROI-to-ROI FC the dependent variable. Results of primary models will be considered significant at $p \leq 0.004$ (Bonferroni correction for twelve ROI-to-ROI connections).

STUDY PROCEDURE DESCRIPTION

5

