60 total participants will complete baseline assessment, alcohol and placebo sessions (30 diagnosed with bipolar disorder and 30 healthy comparison subjects). All subjects will be between 21 and 26 years of age. We plan to include equal numbers of males and females and minorities in proportions representative of the population in the greater Austin area. We expect many subjects will be students at University of Texas. We also expect to recruit approximately 10 participants who will not meet inclusion/exclusion criteria following initial clinical assessment (e.g., they do not meet criteria for bipolar disorder type I). These individuals will be compensated for completing the clinical interview but will not be invited to come in for the baseline scan or the alcohol/placebo MRI session. Total participants to be recruited includes 70 young adults.

b Minimum Age

To input text, click in the light grey area below.

21 years of age

c Maximum Age

To input text, click in the light grey area below.

26 years of age

d Inclusion Criteria

To input text, click in the light grey area below.

Eligibility will be determined by the staff consenting subjects, under the supervision of the Principal Investigator.

Inclusion Criteria:

All Subjects:

1. ages 21-26 years
2. male and female subjects from all racial and minority groups

Subjects with Bipolar Disorder:

1. diagnosis of bipolar disorder type I

7

Total Sample Size

To input text, click in the light grey area below.

Total study participants that will be recruited are 70 young adults (30 participants with bipolar disorder and 30 typically developing comparison young adults will complete the study and estimate 10 participants will not meet inclusion/exclusion criteria following initial clinical interview).

8

Sample size rationale

To input text, click in the light grey area below.

The proposed N in this study has the power to detect medium to large effects. At an alpha=0.05, 30 subjects per group will provide >80% statistical power to detect a within subject ES $d \geq 0.5$ and a between group ES $d \geq 0.7$. This compares favorably with large ESs calculated from between group differences in subjective response to alcohol in youth at risk for bipolar disorder (defined by previous hypomanic experiences; $d > 1.3$) [53]. Our design

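### The connectivity model omits age and sex, the matching variables; if either modifies the alcohol effect, the group-by-condition test is conservative and less powerful, by an unknown and possibly small amount

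*Combined protocol and SAP*

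**What the plan says.** Section 2 (Study Background) says that bipolar participants will be studied "compared to age-and sex-matched healthy comparison participants". Section 3 plans "n=30 per group, 21-26 years of age, 50% women". No pairing procedure, age tolerance or pair identifier is described.

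Section 4 (Data Analysis) has two models:

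- **Aim 1, subjective response:** group, condition and time, "covarying beverage condition order, biological sex, and age with SEAS and DEQ subscale scores as the dependent variables".
- **Functional connectivity:** "We will use a mixed model to examine group by condition by hemisphere (left, right) interactions on ROI-to-ROI FC response to emotional stimuli". The terms are then listed: "Group will be an independent between-subject factor, condition and hemisphere within-subject factors, and ROI-to-ROI FC the dependent variable". No covariate is named. The threshold is p ≤ 0.004, a "Bonferroni correction for twelve ROI-to-ROI connections".

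The plan gives no reason for the difference in covariates. Hypothesis (b) in Section 1 and Aim 2 in Section 3 both concern group differences in change under alcohol relative to placebo. In this model that is an interaction with condition.

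**The concern.** When groups are balanced on a variable by design, that variable adds little or nothing to the sampling error of the group difference. A model that leaves it out still counts its variance as residual. If the variable predicts the quantity being compared, the standard error is too large, the true false-positive rate falls below nominal and power is lost.

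Here the quantity compared is each participant's alcohol-minus-placebo change in connectivity. What matters is therefore whether sex or age predicts that change, not whether it predicts connectivity in general. If one does, the group-by-condition test at p ≤ 0.004 gives up power that two variables already in use for Aim 1 could recover. If matching also turns out imperfect among 60 participants, part of the sex or age difference in the alcohol effect would be read as a group difference.

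**Working it through.** **Inputs.** From the documents: 30 per group; threshold 0.004 (0.05/12 = 0.00417, rounded down); between-group effect size d = 0.7 (Section 8). Assumed: a two-sided test; d = 0.7 applied to the hemisphere-averaged alcohol-minus-placebo change; R², the share of within-group variance in that change explained by sex and age, from 0 to 0.20. The documents give no R².

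**1. The plan's own power statement.** Section 8 says "At an alpha=0.05, 30 subjects per group will provide >80% statistical power" for a between-group d of at least 0.7. A two-sample t-test with 58 df gives 85.0% one-sided and 76.0% two-sided, so the figure reproduces only one-sided. At the connectivity threshold of 0.004, two-sided, power is 39.6%. That is the baseline below.

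**2. Which age and sex terms reach the tested interactions.** For participant i under condition c and hemisphere h, write

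y = β·sexᵢ + γ·ageᵢ + (group, condition and hemisphere terms) + error.

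Sex and age are constant within a participant. In y(alcohol) − y(placebo), β·sexᵢ and γ·ageᵢ subtract out; the same holds for left minus right. One simulated balanced 2×2×2 data set with sex and age main effects shows this. The variance components are illustrative; the cancellation is not:

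| Term | SE, no covariates | SE, additive age + sex |
|---|---|---|
| Group | 0.0407 | 0.0359 |
| Group × condition | 0.04113 | 0.04113 |
| Group × condition × hemisphere | 0.08226 | 0.08226 |

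Additive terms, as in Aim 1, sharpen only the group main effect.

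**3. If sex or age modifies the alcohol effect.** Now the change itself contains δ·sexᵢ + η·ageᵢ. Adjusting for these divides the residual SD by 1/√(1 − R²), that is, multiplies it by √(1 − R²), and uses two df:

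- unadjusted: noncentrality 0.7 × √(30/2) = 2.711, 58 df
- adjusted: noncentrality 2.711/√(1 − R²), 56 df

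| Assumed R² | Noncentrality | Unadjusted power | Adjusted power | Gain (points) |
|---|---|---|---|---|
| 0 | 2.711 | 39.6% | 39.5% | −0.1 |
| 0.05 | 2.782 | 39.6% | 42.1% | 2.5 |
| 0.10 | 2.858 | 39.6% | 45.0% | 5.4 |
| 0.20 | 3.031 | 39.6% | 51.6% | 12.0 |

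Simulation with sex and age distributed identically in the two groups (200,000 runs) gave 38.9% against 45.0% at R² = 0.10, and 38.1% against 51.7% at R² = 0.20.

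**4. False-positive rate without adjustment.** Under exact balance the unadjusted t statistic is shrunk by about √(1 − R²), so the true rate is approximately P(|t₅₈| > 2.998/√(1 − R²)). This is 0.0025 at R² = 0.10 and 0.0014 at R² = 0.20, against a nominal 0.004. The simulation gave 0.0025 and 0.0013 unadjusted, and 0.0039 and 0.0041 adjusted.

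**5. Imperfect matching.** If the groups differ by Δ in the proportion of women, the unadjusted group difference in change is shifted by Δ·δ. The shift is zero if either is zero; age behaves the same way.

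**6. The three-way test.** The same algebra applies to each participant's left-minus-right difference in change, with d and R² redefined for that contrast. The plan gives no effect size for it, so the table covers group-by-condition only.

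**The case against.** The strongest case against the point is that nothing in the documents shows that sex or age modifies the alcohol effect on connectivity. Without that, the loss on the tested interactions is zero. Several design features also limit it: ages span only 21–26, dose is set by gender and weight towards a common target breath alcohol level, and scanning starts once a set ascending-limb reading is reached. The Aim 1 model does not enter its covariates by condition either, so the remedy goes beyond restoring consistency. All of this stands, and it is why the size is given as a range starting at zero.

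It does not remove the point. Dosing to a common level makes a sex difference in response less likely but does not exclude one. The text gives no rule that guarantees balance within each group. Adjustment costs almost nothing if it proves unnecessary, and fixing it in advance stops covariates being chosen after twelve results are seen.

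A reader might infer three stronger things that the documents do not support:

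- **That power is lost whatever the data show.** Step 2 rules this out for the interactions.
- **That calling group an independent factor is an error and a paired analysis is needed.** No individual pairs are described, and the Aim 1 model labels group in the same way while adjusting for sex and age.
- **That the missing covariates explain power near 40%.** That figure comes from sizing the study at alpha 0.05 and testing connectivity at 0.004, which is a separate issue.

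**Conclusion.** The point holds in conditional form. The primary connectivity model leaves out both matching variables, without explanation, while the Aim 1 model includes them. The omission harms the group-by-condition test only if sex or age predicts the alcohol-minus-placebo change. The test is then conservative, and biased as well if the groups are not balanced on that variable.

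Under the stated assumptions, adjustment changes power by −0.1 point at R² = 0, +2.5 at 0.05, +5.4 at 0.10 and +12.0 at 0.20. Given the narrow age range, the low end is plausible. If matching succeeds, the unadjusted estimate is not biased by sex or age. The case for the change rests on its low cost against a possible gain, not on a demonstrated loss.

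**What to change.** In Section 4, under functional connectivity, add biological sex and centred age to the mixed model, each with its interaction with condition. For the three-way test, also add their interactions with condition-by-hemisphere, with the lower-order terms. Equivalently, regress each participant's relevant contrast on group, sex and age: the alcohol-minus-placebo change for group-by-condition, and the left-minus-right difference in that change for the three-way test. Keep p ≤ 0.004. Copying the Aim 1 covariate wording is not enough, because additive terms do not reach these tests. No pair term is needed unless individual pairs are in fact formed. If the sponsor prefers the unadjusted model, the plan should give the reason.

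The cost is a sentence or two of plan text and two error degrees of freedom (58 to 56) on each contrast. If sex and age explain nothing, power falls by about 0.1 percentage point. Both variables are already used in Aim 1, so no new data are needed.

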Official title: Subjective Response to Alcohol and Associated Neural Systems in Bipolar Disorder

NCT number: NCT04063384

Document last approval date: 8/28/2023

Document information: Overall study protocol and change in behavior and functional connectivity (primary outcomes) statistical analysis approach.

1 Research Hypothesis

To input text, click in the light grey area below.

We hypothesize that:

- a) Individuals with bipolar disorder will show a low response to alcohol (decreased self-report of feeling intoxicating and experiencing stimulating/sedative effects of alcohol) and a low response to alcohol will be associated with higher alcohol intake.
- b) Individuals with bipolar disorder, compared to healthy comparison subjects, will show smaller alcohol-induced changes in regional responses of, and functional connections between, the amygdala, striatum, and the dorsal and ventral prefrontal and anterior cingulate cortices. Smaller change in regional responses of, and functional connections between, these regions will be associated with a self-reported low level of response to alcohol.

2 Study Background

To input text, click in the light grey area below.

Disease progression in bipolar disorder is very heterogeneous and our understanding of mechanisms associated with differences in disease progression is limited. Bipolar disorder has a high rate of comorbidity with alcohol use disorders (AUDs) [1-3], with estimates as high as 60% [4]. Comorbidity with AUDs is related to more severe illness outcomes in bipolar disorder, including increased impulsive risk-taking [5-8], more severe mood episodes [9, 10], cognitive deficits [11-13], decreased quality of life and a higher risk for suicide [14-17]. These associations highlight the importance of understanding how this comorbidity develops and the relationship with disease progression in bipolar disorder. However, there has been little study in this area; neuroimaging studies in bipolar disorder have not focused on alcohol use, and related differences in disease progression and, in fact, often exclude subjects with this comorbidity from study.

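### The twelve connectivity tests use a valid single-step Bonferroni threshold; Holm's step-down would keep the same familywise error, never detect fewer connections, and usually gain a few points of power

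*Combined protocol and SAP*

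**What the plan says.** Section 4 (Data Analysis), under the heading on between-group differences in functional connectivity, pairs "limbic/subcortical regions (insula, amygdala, or NAcc) with ventromedial PFC (vmPFC or SCC) and ventrolateral PFC (OFC or IFG.tri) regions". It then states: "We will use a mixed model to examine group by condition by hemisphere (left, right) interactions on ROI-to-ROI FC response to emotional stimuli". Results of the primary models count as significant at p of 0.004 or less, described as a "Bonferroni correction for twelve ROI-to-ROI connections". No step-down rule is mentioned and no simultaneous confidence intervals are planned.

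Section 1 (Research Hypothesis), part b, predicts that the bipolar group "will show smaller alcohol-induced changes in regional responses of, and functional connections between, the amygdala, striatum". Prefrontal and cingulate areas complete its list of regions. It does not name the insula.

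Section 8 (Sample size rationale) gives power at a different level: "At an alpha=0.05, 30 subjects per group will provide >80% statistical power", for a between-group d of 0.7 or more.

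**The concern.** Under the fixed threshold, each connection must pass 0.004 however many of the others have already been declared different. Holm relaxes the threshold after each rejection and keeps the familywise error at the same level without further assumptions. The scientific question is which connections respond differently to alcohol, so any valid additional detection has value. Power per connection is limited at 30 per group, and the difference between the two procedures grows with the number of true effects.

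**Working it through.** **Inputs**
- Twelve tests: 3 limbic/subcortical regions × 4 prefrontal regions = 12 (section 4). Hemisphere is a factor in each model, so it does not double the count.
- Threshold 0.004 (section 4).
- 30 per group (section 3) and between-group d = 0.7 (section 8).
- Assumed: familywise level 0.05, which the connectivity text does not state but 0.004 implies; two-sided tests; 1 to 12 true effects; correlation between tests of 0 to 0.6; d = 0.7 or 1.0.
- Proxy: a two-sample t test on the alcohol-minus-placebo change. The documents give no variance inputs for the three-way interaction that the models name.

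**1. The plan's threshold.** 0.05/12 = 0.00417, which is 0.004 to three decimals. The total alpha spent is 12 × 0.004 = 0.048. If the tests were independent, the familywise error would be 1 − (1 − 0.004)^12 = 0.047. The plan's figure reproduces and errs slightly on the conservative side.

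**2. Holm's thresholds.** Order the p-values and compare the i-th smallest with 0.05/(13 − i): 0.00417, 0.00455, 0.00500, 0.00556, 0.00625, 0.00714, 0.00833, 0.0100, 0.0125, 0.0167, 0.025, 0.05. Stop at the first failure. The first step equals exact Bonferroni and every later step is looser, so Holm's rejections always include Bonferroni's.

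**3. Familywise error with no true effects (40,000 simulated trials).** Both procedures gave 5.1% at correlation 0, which is 5% within simulation error, and 4.0% at correlation 0.5.

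**4. Average power per truly different connection, d = 0.7**

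| True effects | Bonferroni 0.05/12 | Holm | Gain (points) |
|---|---|---|---|
| 1 | 39.8% | 39.9% | 0.1 |
| 3 | 39.9% | 40.9% | 1.0 |
| 4 | about 40% | about 42% | about 2 |
| 6 | 40.2% | 43.0% | 2.8 |
| 8 | about 40% | about 45% | about 5 |
| 12 | 40.1% | 48.8% | 8.7 |

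The rows for 1, 3, 6 and 12 use 40,000 trials at correlation 0. The rows for 4 and 8 use 20,000 trials at correlations 0 and 0.6. With twelve true effects and correlation 0.5, the figures are 40.0% and 50.4%, a gain of 10.4 points.

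At d = 1.0 and correlation 0, power rises from 80.7% to 82.1% (3 true), 80.7% to 84.6% (6 true) and 80.8% to 94.6% (12 true). With 8 true effects, over correlations 0 and 0.6, it rises from about 81% to 86–87%.

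**5. Rounding.** Using 0.004 in place of 0.00417 lowers power at d = 0.7 from 40.1% to 39.6%, about half a point. This is separate from the step-down gain.

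**6. Chance of detecting at least one true effect.** With six true effects at d = 0.7 and correlation 0, it is 95.5% under exact Bonferroni and 95.5% under Holm, against 95.2% at 0.004.

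**7. The larger loss.** At d = 0.7, two-sided power falls from 76% at alpha 0.05 to 40% at 0.004. The effect detectable with 80% power rises from d = 0.74 to d = 1.00. With eight true effects Holm reaches about 45%, still 76 − 45 = 31 points short.

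**8. How many connections the hypothesis covers.** Hypothesis b names the amygdala and striatum on the limbic/subcortical side. The nucleus accumbens falls under striatum and the insula is not named. That leaves at most 2 × 4 = 8 of the twelve connections.

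**The case against.** The strongest reply is that nothing here is wrong. The plan prespecifies a valid familywise correction with the right count and the right threshold, and choosing between two valid procedures is a matter of preference. That stands, and it is why this is offered as an improvement. A single fixed threshold also has merits: it is simple, each connection's verdict does not depend on the other eleven p-values, and it pairs with simple simultaneous intervals. A claim that Bonferroni brings no benefit would go too far, although the plan does not use such intervals.

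A reader might infer from the network-wide wording of hypothesis b that all twelve connections are expected to differ, and so quote the gain of 9 to 10 points. The documents do not support this. They do not say how many connections differ, and the four insula connections lie outside the stated hypothesis.

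The power figures describe group-by-condition change, while the model names group by condition by hemisphere. For that term, a true effect would be a lateralised group difference, which section 1 does not predict. The figures therefore show the order of magnitude and are not the power of the named test. Holm's inclusion of every Bonferroni rejection does not depend on the proxy.

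**Conclusion.** The point holds as an efficiency improvement. Holm gives the same 5% familywise error under any dependence and never fewer detections than the planned rule. At d = 0.7 the gain in power per connection is under 1 point with one true effect, about 2 points with four and about 5 points with eight, the upper limit of what hypothesis b covers. These sizes rest on the assumed number of true effects, 30 completers per group and the two-group proxy.

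A reader might also infer that Holm would restore the power claimed in section 8. It would not. It adds connections after the first rejection, leaves the chance of any finding essentially where it was, and recovers only a small part of the loss from testing at 0.004.

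**What to change.** Make these changes to the connectivity text in section 4 before results are seen:

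1. Name the single model term per connection whose p-value enters the procedure, and say how lower-order terms are handled. The Aim 1 text has a rule for dropping interactions; the connectivity text has none. Holm needs exactly one p-value per connection.
2. Replace the fixed 0.004 with Holm across the twelve p-values at familywise 0.05, comparing the ordered values with 0.05/12, 0.05/11, ..., 0.05/1 and stopping at the first failure.
3. Report Holm-adjusted p-values for all twelve connections.

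The cost is a few sentences, with no new data and no loss of error control. Matching simultaneous confidence intervals are less simple than under Bonferroni, but the plan specifies none.
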